9.9.2 Numerical comparison of annualized relapse rate (ARR)

As a secondary objective the ARR will be compared between patients treated with ofatumumab or placebo. We evaluated the probability to observe a treatment effect in favor of ofatumumab, as defined by an ARR-ratio (ofatumumab/placebo) less than 1 in the overall population. The following assumptions were made for this evaluation:

- 60 subjects in total are randomized 2:1 to ofatumumab or placebo.
- The true ARRs are 0.4 in the placebo arm, and 0.16 in the ofatumumab arm.

- The dispersion parameter, k, is 0.1.
- The follow-up period is 6 months.

Under these settings, the probability to observe a lower ARR in patients treated with ofatumumab compared with placebo is > 80%.

10 Ethical considerations

10.1 Regulatory and ethical compliance

This clinical study was designed and shall be implemented, executed and reported in accordance with the International Council on Harmonization of Technical Requirements for Registration of Pharmaceuticals for Human Use (ICH) Harmonized Tripartite Guidelines for Good Clinical Practice, with applicable local regulations (including European Directive 2001/20/EC, US CFR 21, and Japanese Ministry of Health, Labor, and Welfare), and with the ethical principles laid down in the Declaration of Helsinki.

10.2 Informed consent procedures

Eligible patients/subjects may only be included in the study after providing (witnessed, where required by law or regulation), IRB/IEC-approved informed consent, or, if applicable after such consent has been provided by a legally acceptable representative(s) of the patient. Informed consent must be obtained before conducting any study-specific procedures (e.g. all of the procedures described in the protocol). The process of obtaining informed consent must be documented in the patient source documents.

Novartis will provide to investigators in a separate document a proposed informed consent form that complies with the ICH GCP guideline and regulatory requirements and is considered appropriate for this study. Any changes to the proposed consent form suggested by the investigator must be agreed to by Novartis before submission to the IRB/IEC, and a copy of the approved version must be provided to the Novartis monitor after IRB/IEC approval.

Women of child bearing potential must be informed that taking the study treatment may involve unknown risks to the fetus if pregnancy were to occur during the study and agree that in order to participate in the study they must adhere to the contraception requirement for the duration of the study. If there is any question that the patient will not reliably comply, they must not be entered in the study.

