3.1.3 Safety FU period

The **Safety FU period** ([Table 6-2](#)) will be applicable for the following patients:

- Patients who complete this study and do not enter the planned umbrella long-term extension study
- Patients who prematurely discontinue study treatment in Core or Extension part

All Safety FU visits must be scheduled relative to the date of EOS visit.

[figure not shown]
These patients will be followed for a total of at least 36 weeks after study drug discontinuation (by 36 weeks the vast majority of patients are expected to have repleted their circulating B-cells, see [Section 3.3](#)).

A longer than 36 weeks of post-treatment Safety FU period will be required for patients who have not repleted their B-cells (i.e. B-cells not back to baseline value or to lower limit of normal (LLN) whichever comes first as determined by central lab) at 36 weeks.

These patients will continue to be followed with 12-weekly assessments until their B-cell counts have repleted. To protect the study blind, the assessment of B-cell counts will be performed centrally and the Investigators and Sponsor study team will only be informed of whether or not continued follow-up is necessary.

Patients who have initiated therapy with another disease modifying/immunosuppressive therapy before the end of the 36-week follow-up will not be monitored beyond 36 weeks.

Figure 3-1 Study design

* Patients randomized to placebo in the Double-blind treatment period will receive ofatumumab 20 mg sc at Week 24, 25 and 26 as loading dose regimen. Patients randomized to ofatumumab in the Double-blind treatment period will receive ofatumumab 20 mg sc at Week 24 and the matching placebo sc at Week 25 and 26. In all patients, the extension part starts with the Week 24 injection.

** Patients who prematurely discontinue study drug or patients who do not enter the umbrella extension study will enter the Safety FU period following their EOS visits.

*** Umbrella extension study (planned) will be conducted under separate protocol.

Data cut-off 1 is defined as the date the last patient completes all the assessments for Week 24.

Data cut-off 2 is defined as the date the last patient completes all the assessments for Week 48.

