4.2 Exclusion criteria

Patients fulfilling **any** of the following criteria are not eligible for inclusion in this study. No additional exclusions may be applied by the Investigator, in order to ensure that the study population will be representative of all eligible patients.

1. Patients suspected of not being able or willing to cooperate or comply with study protocol requirements in the opinion of the Investigator
2. Patients with primary progressive MS ([Polman et al 2011](#)) or SPMS without disease activity ([Lublin et al 2014](#))
3. Patients meeting criteria for neuromyelitis optica ([Wingerchuk et al 2006](#))
4. Pregnant or nursing (lactating) women, where pregnancy is defined as the state of a female after conception and until the termination of gestation, confirmed by a positive human chorionic gonadotropin (hCG) laboratory test.
5. Women of child-bearing potential, defined as all women physiologically capable of becoming pregnant, unless they are using highly effective methods of contraception during dosing and for at least 12 months after stopping study medication. Highly effective contraception methods include:
 - Total abstinence (when this is in line with the preferred and usual lifestyle of the subject, if accepted by the local regulation). Periodic abstinence (e.g., calendar,

ovulation, symptothermal, post-ovulation methods) and withdrawal are not acceptable methods of contraception.

- Female sterilization (have had surgical bilateral oophorectomy with or without hysterectomy), total hysterectomy or tubal ligation at least six weeks before taking investigational drug. In case of oophorectomy alone, only when the reproductive status of the woman has been confirmed by follow-up hormone level assessment
- Male partner sterilization (at least 6 months prior to Screening). For female patients on the study, the vasectomized male partner should be the sole partner.
- Use of oral (estrogen and progesterone), injected or implanted hormonal methods of contraception or placement of an intrauterine device or intrauterine system or other forms of hormonal contraception that have comparable efficacy (failure rate < 1%), for example hormone vaginal ring or transdermal hormone contraception. In case of use of oral contraception, women should have been stable on the same pill for a minimum of 3 months before taking study drug.

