5.6 Study completion and discontinuation

5.6.1 Study completion and post-study treatment

A patient will complete this study when the patient has completed the End of Study (EOS) visit.

Patients, who complete the EOS visit ([Table 6-1](#)) on study drug, may be eligible for inclusion in the planned umbrella extension study (under separate protocol).

Either patients who complete their EOS visits on study drug and do not enter the umbrella extension study (planned) or patients who prematurely discontinue study drug and complete their EOS visits will enter the Safety FU period ([Table 6-2](#)) for continued follow-up.

The Safety FU will complete when all patients who entered have been followed for the stipulated period of time (for at least 36 weeks after study drug discontinuation) (see [Section 3.1.3](#)) or have withdrawn participation prematurely.

The Investigator must provide follow-up medical care for all patients who are prematurely withdrawn from the study, or must refer them for appropriate ongoing care.

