13. In case of relapse, if an MRI for efficacy has been scheduled within 14 days of the initiation of steroid treatment, the MRI should be performed before steroid treatment is initiated. No MRI for efficacy should be performed while a patient is on steroid therapy for relapse and within 14 days upon termination of steroid therapy.
14. MRI scan at the EOS is needed if there was no MRI scan in the last 3 months.
15. Including corticosteroids used to treat MS relapse; any newly started MS treatment as applicable (for patients who have discontinued study medications).

16. Applicable for patients who take study treatment by home-administration. Telephone interview by site staff should take place around time of the sc self/home injection to query about any new or worsening symptoms warranting an unplanned visit, injection reactions, results of home pregnancy testing, compliance with contraception requirements as applicable.
17. Patients will receive sc injections of Double-blind treatment period on Day 1, Day 7 (\pm 1 day), Day 14 (\pm 1 day), Week 4 (\pm 3 days), Week 8 (\pm 3 days), Week 12 (\pm 3 days), Week 16 (\pm 3 days) and Week 20 (\pm 3 days), the sc injection of the Double-blind loading dose period at Week 24 (\pm 3 days), Week 25 (\pm 1 day) and Week 26 (\pm 1 day), and the Open-label ofatumumab sc injection from Week 28 (\pm 3 days), followed by every 4 weeks (\pm 3 days).
18. Labs must be drawn to allow adequate time for results to be obtained before randomization to ensure patient's eligibility
19. Patients do not have to visit the site at Week 25 and 26 if they are permitted to administer the sc injection at home at investigator's discretion.
20. If the trial is extended beyond Week 72, every 12 weeks visit (Week 84, 96 and so forth) will be performed with same measurements as at Week 60, 72 and so forth.

[REDACTED]

[REDACTED]

Table 6-2 Assessment schedule for Safety Follow-up period

Visit Week ¹ (relative to EOS)	+W12	+W24	+W36	Every 12 weeks ²	End of Safety-FU ³
Visit Number	410	420	430	440/4XX	2999
Visit window (days)	±14	±14	±14	±14	
AEs	X	X	X	X	X
Concomitant Meds*	X	X	X	X	X
Vital Signs	X	X	X	X	X
eCSSRS	X	X	X	X	X
Urine pregnancy test ⁴	X	X	X	X	X
Contraception status	X	X	X	X	X
Laboratory sample including sample for B-cells and T-cells	X	X	X	X	X
Sample for Total IgG, IgM	X	X	X	X	X
MS Relapse	X	X	X	X	X
EDSS	X	X	X	X	X

W=week.

1. Time measured from the EOS visit.

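### The protocol gives two different end dates for the contraception requirement: 12 months after stopping study medication in eligibility, and the length of the study in the consent section.

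*Protocol*

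**What the plan says.** Section 4.2, exclusion 5, bars women of child-bearing potential unless "they are using highly effective methods of contraception during dosing and for at least 12 months after stopping study medication". The key exclusion criteria in the protocol summary give the same 12 months.

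Section 10.2 tells sites what these women must be told and must agree to. They are to hear of unknown fetal risks from a pregnancy during the study, and to agree that "they must adhere to the contraception requirement for the duration of the study". No period after the last dose is mentioned.

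Three other places bear on how long the study lasts for a patient:

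- Section 5.6.1: "A patient will complete this study when the patient has completed the End of Study (EOS) visit". Safety FU comes after that visit.
- Section 3.1.3: "These patients will be followed for a total of at least 36 weeks after study drug discontinuation". The extension rule is "A longer than 36 weeks of post-treatment Safety FU period will be required for patients who have not repleted their B-cells". Patients who start another disease-modifying or immunosuppressive therapy "before the end of the 36-week follow-up will not be monitored beyond 36 weeks".
- Table 6-2, footnote 1, on the follow-up visits: "Time measured from the EOS visit". The table schedules contraception review and urine pregnancy tests at each Safety FU visit, and footnote 4 adds monthly home tests between visits.

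Section 7.6 requires every pregnancy after consent to be reported within 24 hours of the site learning of it. It sets no end date.

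**The concern.** The post-dosing part of exclusion 5 cannot be verified at entry; it can be met only by a commitment the woman makes then. Section 10.2 is where the protocol describes that commitment, and it attaches a different period. An investigator or ethics committee checking a consent form against section 10.2 alone could accept wording without the 12 months, whereas one checking against section 4.2 could not.

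What is at stake is the clarity of a safeguard against fetal exposure. The point does not touch the primary endpoint, blinding, alpha, power or any analysis.

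**Working it through.** The plan gives no figure to reproduce here. The check sets the passages side by side and converts the periods to days.

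**Inputs**

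- Contraception period in eligibility: dosing plus 12 months (section 4.2 and protocol summary).
- Contraception period in consent: the study's duration (section 10.2).
- Minimum Safety FU: 36 weeks (section 3.1.3), which is 36 × 7 = 252 days.
- Length of a month: 28 days in protocol section 6 (for the visit schedule), 30 days in SAP 2.1.1, or a calendar year of 365 days. The protocol does not say which applies to contraception.
- Window for Safety FU visits: ±14 days (Table 6-2).
- Time from last dose to EOS: not fixed in the protocol. I assume 0 to 31 days, the upper end being one dosing interval plus its window (28 + 3).

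**If the study ends with a 36-week Safety FU.** Gap = 12 months − 252 days, taking EOS on the day of the last dose:

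| Month length | 12 months (days) | Gap (days) | Gap (weeks) |
|---|---|---|---|
| 28 days | 336 | 336 − 252 = 84 | 12.0 |
| 30 days | 360 | 360 − 252 = 108 | 15.4 |
| Calendar year | 365 | 365 − 252 = 113 | 16.1 |

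**Allowing for the EOS delay and the visit window.** Last follow-up day after the last dose = delay + 252 ± 14.

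- Smallest gap: 336 − (31 + 252 + 14) = 39 days, or 5.6 weeks.
- Largest gap: 365 − (0 + 252 − 14) = 127 days, or 18.1 weeks. This needs a final visit at the early edge of its window.

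The gap does not close within these assumptions. At the nominal visit day, EOS would have to fall 84 to 113 days after the last dose to close it.

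**If the study ends at EOS.** Gap = 12 months − delay, which runs from 336 − 31 = 305 days to 365 − 0 = 365 days.

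**Patients followed beyond 36 weeks.** One further 12-week interval takes follow-up to 36 + 12 = 48 weeks, or 336 days after EOS. That equals 12 months of 28 days and is 24 or 29 days short of 360 or 365 days if EOS is on the day of the last dose. The extension depends on B-cell repletion and is not linked to contraception. Section 3.3 expects the vast majority to replete within 9 months, so ending near 36 weeks is the usual course.

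**The case against.** The best reply is that section 10.2 refers to a requirement defined elsewhere. Only exclusion 5 and the summary define it, and both say 12 months, so section 10.2 may be no more than an incomplete cross-reference. A woman who follows exclusion 5 will usually satisfy section 10.2 as well. Exclusion 5 also gates entry: section 5.3 has the investigator confirm all criteria before randomization, and section 10.2 keeps out anyone whose compliance is in doubt.

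Much of this stands. A reader might infer that section 10.2 permits contraception to stop at study end; it does not say so. But the sentence does more than refer back. It attaches its own period, and that period differs from the one in exclusion 5. The entry gate does not settle which period a woman is asked to accept.

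Other stronger inferences are not supported:

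- **That women are consented to the shorter period.** Section 10.2 says the proposed consent form is a separate document. It is not available here and may already state 12 months.
- **That a pregnancy in the gap would go unrecorded.** Scheduled tests and reviews do stop with Safety FU, but the reporting duty in section 7.6 has no cut-off. A pregnancy that the site learns of must still be reported.
- **That the shorter schedule of tests is itself an error.** Nothing in the protocol says testing must last as long as the contraception commitment.
- **That the number of women affected can be read from the 10% dropout allowance in section 9.9.** That figure is a sample-size allowance. It does not count women, or patients entering Safety FU.

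**Conclusion.** The inconsistency is in the current protocol text. Eligibility and consent give different end dates for one requirement. On the Safety FU reading the consent period can end about 12 to 16 weeks before the eligibility period, or 5.6 to 18.1 weeks once visit windows and an assumed EOS delay of 0 to 31 days are allowed for. On the EOS reading almost the whole 12 months falls outside it.

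These sizes apply to patients whose follow-up ends at 36 weeks. They rest on reading the study's duration as the patient's own participation. Patients who enter the umbrella extension come under another protocol and are not covered. The documents do not show which end date was intended, and this review takes no position on it.

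**What to change.** Reconcile the protocol summary, section 4.2 (exclusion 5) and section 10.2 so that one end date for the contraception requirement, with the point from which it is counted, appears in both eligibility and consent. Check that the consent form states the same. The choice of duration rests with the sponsor.

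The cost is about one sentence in the protocol, handled through the amendment process in section 11.1, and a matching line in the consent form if it differs. No visits, tests, patients or analyses change.

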10.3 Responsibilities of the investigator and IRB/IEC

Before initiating a trial, the Investigator/institution must obtain approval/favorable opinion from the Institutional Review Board/Independent Ethics Committee (IRB/IEC) for the trial protocol, informed consent form, consent form updates, subject recruitment procedures (e.g., advertisements) and any other written information to be provided to patients/subjects. Prior to study start, the Investigator is required to sign a protocol signature page confirming his/her agreement to conduct the study in accordance with these documents and all of the instructions and procedures found in this protocol and to give access to all relevant data and records to Novartis monitors, auditors, Novartis Quality Assurance representatives, designated agents of Novartis, IRBs/IECs, and regulatory authorities as required. If an inspection of the clinical site

is requested by a regulatory authority, the Investigator must inform Novartis immediately that this request has been made.

10.4 Publication of study protocol and results

The key design elements of this protocol will be posted in a publicly accessible database such as clinicaltrials.gov. In addition, upon study completion and finalization of the study report the results of this trial will be either submitted for publication and/or posted in a publicly accessible database of clinical trial results.

10.5 Quality Control and Quality Assurance

Novartis maintains a robust Quality Management (QM) system that includes all activities involved in quality assurance and quality control, including the assignment of roles and responsibilities, the reporting of results, and the documentation of actions and escalation of issues identified during the review of quality metrics, incidents, audits and inspections.

Audits of Investigator sites, vendors, and Novartis systems are performed by Novartis Pharma Auditing and Compliance Quality Assurance (CQA), a group independent from those involved in conducting, monitoring or performing quality control of the clinical trial. The clinical audit process uses a knowledge/risk based approach.

Audits are conducted to assess GCP compliance with global and local regulatory requirements, protocols and internal Standard Operating Procedures (SOPs), and are performed according to written Novartis processes.

11 Protocol adherence

This protocol defines the study objectives, the study procedures and the data to be collected on study participants. Additional assessments required to ensure safety of patients/subjects should be administered as deemed necessary on a case by case basis. Under no circumstances including incidental collection is an Investigator allowed to collect additional data or conduct any additional procedures for any purpose involving any investigational drugs under the protocol, other than the purpose of the study. If despite this interdiction, data, information, observation would be incidentally collected, the investigator shall immediately disclose it to Novartis and not use it for any purpose other than the study, except for the appropriate monitoring on study participants.

Investigators ascertain they will apply due diligence to avoid protocol deviations. If an Investigator feels a protocol deviation would improve the conduct of the study this must be considered a protocol amendment, and unless such an amendment is agreed upon by Novartis and approved by the IRB/IEC and health authorities, where required, it cannot be implemented.

INR= International normalized ratio

Table 13-2 Follow-Up Requirements for Liver Events and Laboratory Triggers

Criteria	Actions required	Follow-up monitoring
Potential Hy's Law case ^a	Discontinue the study treatment immediately Hospitalize, if clinically appropriate Establish causality Record AE/SAE and any contributing factors (concomitant medications, other co-morbid conditions/procedures) in the appropriate CRFs	ALT, AST, TBL, Alb, PT/INR, AP and GGT until resolution ^c (frequency at Investigator discretion)
ALT or AST $> 8 \times \text{ULN}$	Discontinue the study treatment immediately Hospitalize if clinically appropriate Establish causality Record AE/SAE and any contributing factors (concomitant medications, other co-morbid conditions/procedures) in the appropriate CRFs	ALT, AST, TBL, Alb, PT/INR, AP and GGT until resolution ^c (frequency at Investigator discretion)

Criteria	Actions required	Follow-up monitoring
> 3 × ULN and INR > 1.5	Discontinue the study treatment immediately Hospitalize, if clinically appropriate Establish causality Record AE/SAE and any contributing factors (concomitant medications, other co-morbid conditions/procedures) in the appropriate CRFs.	ALT, AST, TBL, Alb, PT/INR, AP and GGT until resolution ^c (frequency at Investigator discretion)
> 5 to ≤ 8 × ULN	Repeat LFT within 48 hours If elevation persists, continue follow-up monitoring If elevation persists for more than 2 weeks, discontinue the study drug Establish causality Record AE/SAE and any contributing factors (concomitant medications, other co-morbid conditions/procedures) in the appropriate CRFs	ALT, AST, TBL, Alb, PT/INR, AP and GGT until resolution ^c (frequency at Investigator discretion)
> 3 × ULN accompanied by symptoms ^b	Discontinue the study treatment immediately Hospitalize if clinically appropriate Establish causality Record AE/SAE and any contributing factors (concomitant medications, other co-morbid conditions/procedures) in the appropriate CRFs	ALT, AST, TBL, Alb, PT/INR, AP and GGT until resolution ^c (frequency at Investigator discretion)
> 3 to ≤ 5 × ULN (patient is asymptomatic)	Repeat LFT within the next week If elevation is confirmed, initiate close observation of the patient	Investigator discretion Monitor LFT within 1 to 4 weeks
ALP (isolated)	Repeat LFT within 48 hours If elevation persists, establish causality Record AE/SAE and any contributing factors (concomitant medications, other co-morbid conditions/procedures) in the appropriate CRFs	Investigator discretion Monitor LFT within 1 to 4 weeks or at next visit
TBL (isolated)	Repeat LFT within 48 hours If elevation persists, discontinue the study drug immediately Hospitalize if clinically appropriate Establish causality Record AE/SAE and any contributing factors (concomitant medications, other co-morbid conditions/procedures) in the appropriate CRFs	ALT, AST, TBL, Alb, PT/INR, AP and GGT until resolution ^c (frequency at Investigator discretion) Test for hemolysis (e.g., reticulocytes, haptoglobin, unconjugated [indirect] bilirubin)

Criteria	Actions required	Follow-up monitoring
> 1.5 to \leq 2 \times ULN (patient is asymptomatic)	Repeat LFT within the next week If elevation is confirmed, initiate close observation of the patient	Investigator discretion Monitor LFT within 1 to 4 weeks or at next visit
Jaundice	Discontinue the study treatment immediately Hospitalize the patient Establish causality Record AE/SAE and any contributing factors (concomitant medications, other co-morbid conditions/procedures) in the appropriate CRFs	ALT, AST, TBL, Alb, PT/INR, AP and GGT until resolution ^c (frequency at Investigator discretion)
Any AE potentially indicative of a liver toxicity*	Consider study treatment interruption or discontinuation Hospitalization if clinically appropriate Establish causality Record AE/SAE and any contributing factors (concomitant medications, other co-morbid conditions/procedures) in the appropriate CRFs	Investigator discretion

^aElevated ALT/AST > 3 \times ULN and TBL > 2 \times ULN but without notable increase in AP to > 2 \times ULN

^b(General) malaise, fatigue, abdominal pain, nausea, or vomiting, or rash with eosinophilia

^cResolution is defined as an outcome of one of the following: (1) return to baseline values, (2) stable values at three subsequent monitoring visits at least 2 weeks apart, (3) remain at elevated level after a maximum of 6 months, (4) liver transplantation, and (5) death.

PT=prothrombin time

14 Appendix 2: Specific Renal Alert Criteria and Actions

Table 14-1 Specific Renal Alert Criteria and Actions

Serum Event	
Serum creatinine increase 25-49% compared to baseline	Confirm 25% increase after 24-48 hours Follow-up within 2-5 days
Acute Kidney Injury: Serum creatinine increase ≥ 50% compared to baseline	Follow-up within 24-48h if possible Consider study treatment interruption Consider patient hospitalization/specialized treatment
Urine Event	
New dipstick proteinuria ≥ 1+ Albumin- or Protein-creatinine ratio increase ≥ 2-fold Albumin-creatinine ratio (ACR) ≥ 30 mg/g or ≥ 3 mg/mmol; Protein-creatinine ratio (PCR) ≥ 150 mg/g or > 15 mg/mmol	Confirm value after 24-48 hours Perform urine microscopy Consider study treatment interruption/or discontinuation
New dipstick glycosuria ≥ 1+ not due to diabetes	Blood glucose (fasting) Perform serum creatinine, ACR
New dipstick hematuria ≥ 1+ not due to trauma or menstruation	Urine sediment microscopy Perform serum creatinine, ACR
For all renal events:	
Record AE/SAE and any contributing factors (concomitant medications, other co-morbid conditions/procedures) in the appropriate CRFs.	
Monitor patient regularly (frequency at Investigator's discretion) until either: Event resolution: sCR within 10% of baseline or protein-creatinine ratio within 50% of baseline, or Event stabilization: sCR level with ±10% variability over last 6 months or protein-creatinine ratio stabilization at a new level with ±50% variability over last 6 months.	

15 Appendix 3: Safety monitoring Guidance

15.1 Guidance on monitoring of patients with symptoms of neurological deterioration suggestive of PML

Should a patient develop any unexpected neurological or psychiatric symptom/signs in the opinion of Investigator (e.g. cognitive deficit, behavioral changes, cortical visual disturbances or any other neurological cortical symptoms/signs any symptom/sign suggestive of an increase of intracranial pressure) or accelerated neurological deterioration, the Investigator should schedule a complete physical and neurological examination and an MRI as soon as possible before beginning any steroid treatment. Conventional MRI as defined in the protocol as well as additional scanning such as Fluid-Attenuated Inversion Recovery (FLAIR) and Diffusion-weighted imaging (DWI) sequences are recommended to aid in differential diagnosis. The MRI must be evaluated by the local radiologist/neurologist. The Investigator will contact the Medical Advisor at Novartis to discuss findings and diagnostic possibilities as soon as possible. A copy of the unplanned MRI should be sent to the MRI Evaluation Center designated by the Sponsor as soon as possible. AE/SAEs need to be filed as appropriate.

If the MRI shows new MS lesions consistent with an MS relapse, assessment and treatment of the relapse will be performed as described in the protocol ([Section 6.4.1](#) and [Section 5.5.6](#), respectively). In case of new findings in the MRI images in comparison with the previous available MRI which are not compatible with MS lesions, the study drug will be discontinued and other diagnostic evaluations need to be performed at the discretion of the Investigator. If new lesions are detected on the MRI which may be infectious in origin it is recommended to collect a cerebrospinal fluid sample if indicated. Analysis of the Cerebrospinal fluid (CSF) sample including cellular, biochemical, PCR, and microbiological analysis (e.g. herpes virus, JC virus) to confirm/exclude an infection should be performed. In the event of suspected CNS infection (PML), a CSF aliquot should be sent to a central laboratory (designated by the Sponsor) for confirmatory testing.

Only after the evaluations have excluded diagnoses other than MS and after discussion with the Medical Advisor at Novartis, the study drug may be restarted.

